9.1.1. Multiplicity Adjustment

The primary and the key secondary objectives will be evaluated align to both the treatment-regimen estimand and the efficacy estimand. No multiplicity adjustment will be made for conducting analysis aligned to the two estimands.

A prespecified graphical scheme (Bretz et al. 2009; Bretz et al. 2011) will be implemented to control the family-wise error rate at a 2-sided alpha level of 0.05. This graphical approach is a closed testing procedure; hence, it strongly controls the family-wise error rate across all endpoints (Bretz et al. 2009; Bretz et al. 2011; Alosh et al. 2014).

The testing scheme will be fully detailed in the SAP. The testing scheme will be finalized before database lock.

9.2. Analyses Sets

For purposes of analysis, the following analysis sets are defined.

| Population/Analysis Set | Description |
|---|--|
| Screened population | All participants who signed informed consent |
| Randomized population | All participants who are randomly assigned to a treatment group. |
| Modified intention-to-treat (mITT) population | All randomly assigned participants who are exposed to at least 1 dose of study intervention. |
| Efficacy analysis set (EAS): This analysis set will be used to estimate the efficacy estimand for all efficacy objectives | Data obtained during Study Period II from the mITT population, excluding data after initiating rescue antihyperglycemic medication or stopping study intervention. |

| | |
|---|--|
| Full analysis set: This analysis set will be used to estimate the treatment-regimen estimand for the primary and key secondary objectives | Data obtained during Study Period II from the mITT population, regardless of adherence to study intervention or initiation of rescue antihyperglycemic medication. |
| Safety analysis set (SS): This analysis set will be used to assess the safety of study treatment | Data obtained during Study Periods II or III from the mITT population, regardless of adherence to study intervention or initiation of rescue antihyperglycemic medication. |

9.3. Statistical Analyses

9.3.1. General Considerations

Handling of missing, unused, and spurious data are addressed prospectively in the overall statistical methods described in the protocol (section 9.3) and in the SAP, where appropriate. Adjustments to the planned analyses will be described in the final clinical study report (CSR).

Statistical analysis of this study will be the responsibility of Lilly or its designee.

Any change to the data analysis methods described in the protocol will require an amendment ONLY if it changes a principal feature of the protocol. Any other change to the data analysis methods described in the protocol, and the justification for making the change, will be described in the SAP or CSR. Additional exploratory analyses of the data will be conducted as deemed appropriate.

Unless otherwise noted, all tests of treatment effects will be conducted at a 2-sided alpha level of 0.05, and the confidence interval will be calculated at 95%, 2-sided. In statistical summaries and analyses, all data will be analyzed by randomized treatment assignment. Participants will be analyzed according to the treatment they were randomly assigned to, regardless of the treatment actually received.

Baseline is defined as the last non-missing measurement recorded on or before the randomization visit, prior to first dose of treatment, unless otherwise specified.

Efficacy analyses will use the full analysis set (FAS) to evaluate the treatment-regimen estimand and the efficacy analysis set to evaluate the efficacy estimand. Safety will be assessed using safety analysis set (SS). Selected safety analyses may be conducted after excluding data on rescue therapy or data after starting another antihyperglycemic medication.

Summary statistics for continuous measures will include sample size, mean, standard deviation (SD), median, minimum, and maximum. The analysis model to make comparisons among treatment groups relative to continuous measurements assessed over time will be a mixed model for repeated measures (MMRM) with terms:

- treatment,
- visit,
- treatment-by-visit interaction,
- any past prior use (yes or no) of any antihyperglycemic medication,
- baseline HbA1c category [$\leq 8.5\%$ (≤ 69 mmol/mol) or $> 8.5\%$ (> 69 mmol/mol)],
- and baseline measurement as a covariate.

For analyses with HbA1c, the baseline HbA1c category will not be included in the model. An unstructured covariance structure will model the relationship of within-patient errors.

The Kaplan-Meier method will be used for estimation of cumulative event-free survival rates over time, and cox proportional hazards regression analysis will be used to compare hazard rates among treatments.

Summary statistics for categorical measures (including categorized continuous measures) will include sample size, frequency, and percentages. Fisher's exact test will be used to examine the treatment difference in categorical outcomes. Logistic regression may be used to examine the treatment difference in binary efficacy outcomes. The negative binomial regression model will be used for the treatment comparison of discrete count measures if deemed appropriate.

Other statistical methods may be used, as appropriate, and details will be documented in the SAP.

9.3.2. Treatment Group Comparability

9.3.2.1. Participant Disposition

Frequency counts and percentages of all participants screened, randomized, and receiving at least 1 dose of study intervention will be presented by treatment groups. A listing of randomized participants not receiving study intervention will be provided. Of the participants in the randomized population, frequency, counts and percentages of participants completing the study, prematurely discontinuing the study, including the reason for premature discontinuation; and prematurely discontinuing study intervention including the reason for premature discontinuation of study intervention will be presented by treatment group. A Kaplan-Meier analysis of time from randomization to premature discontinuation from study by treatment group will be provided.

9.3.2.2. Participant Characteristics

Demographics will be summarized by treatment group using the randomized population. Medical history and concomitant illness will be summarized using the mITT population.

9.3.2.3. Concomitant Therapy

Concomitant medications will be summarized by anatomical therapeutic chemical classification and treatment group using the mITT population. In particular, the time of initiation of rescue therapy for severe, persistent hyperglycemia will be analyzed and summarized.

9.3.2.4. Treatment Compliance

A Kaplan-Meier analysis of time from randomization to premature study intervention discontinuation by treatment group will be provided.

Treatment compliance is defined as taking at least 75% of required injections of study intervention. Frequency counts and percentages of participants compliant to study intervention will be summarized by treatment arm using the mITT population.

9.3.3. Primary Endpoint(s) Analysis

The primary endpoint for this study is HbA1c change from baseline at Week 40. This endpoint will be used to evaluate the primary objective of the study for both the treatment-regimen and efficacy estimands (Section 3).

The alternative hypothesis corresponding to the primary objective is as follows: tirzepatide 5 mg, and/or 10 mg, and/or 15 mg is superior to placebo with respect to HbA1c change from baseline at Week 40 (Section 9.1).

The primary efficacy analysis will be guided by the “treatment-regimen” estimand defined in Section 3. This assessment will analyze change from baseline in HbA1c to Week 40 using an analysis of covariance (ANCOVA) with terms: treatment, any past prior use (yes or no) of any antihyperglycemic medication, and baseline HbA1c as a covariate. The ANCOVA analysis will be conducted using FAS (section 9.2). Missing HbA1c values at Week 40 will be imputed using multiple imputation. Details regarding missing data will be included in the SAP. Statistical inference over multiple imputations will be guided by the method proposed by [Rubin \(1987\)](#).

To explore the treatment efficacy without the influence of rescue therapy, the primary endpoint will be conducted on the “efficacy” estimand. This assessment will be conducted using efficacy analysis set (EAS) dataset (section 9.2). The primary analysis model for HbA1c measurements over time will be a MMRM. The response variable of MMRM will be change in HbA1c values from baseline obtained at each scheduled postbaseline visit. The independent variables of the MMRM model are treatment, visit, and treatment-by-visit interaction, any past prior use (yes or no) of any antihyperglycemic medication, baseline HbA1c and baseline HbA1c-by-visit interaction. Missing data will be addressed by the MMRM model under missing at random assumption. No explicit imputation methods for missing data will be employed.

An unstructured covariance structure will model the relationship of within-patient errors. If the analysis fails to converge, the following variance-covariance matrix will be used (in order) until convergence is achieved: heterogeneous compound symmetry, compound symmetry, and first-order autoregressive. The Kenward-Roger approximation will be used to estimate denominator degrees of freedom.

9.3.4. Secondary Endpoints Analysis

[figure not shown]
The secondary study objectives subject to type 1 error rate control are as follows:

- Superiority of tirzepatide dose(s) to placebo relative to proportion of participants achieving the target value of HbA1c <7.0% (<53 mmol/mol) at Week 40
- Superiority of tirzepatide dose(s) to placebo relative to change in FSG (central laboratory) at Week 40
- Superiority of tirzepatide dose(s) to placebo relative to proportion of participants achieving the target value of HbA1c ≤6.5% (≤48 mmol/mol) at Week 40
- Superiority of tirzepatide dose(s) to placebo relative to change in body weight from baseline to Week 40
- Superiority of tirzepatide dose(s) to placebo relative to proportion of participants achieving the target value of HbA1c <5.7% (<39 mmol/mol) at Week 40

The type 1 error-controlled strategy for the primary and secondary endpoints will be described in the SAP. Key secondary objectives will be evaluated based on the treatment-regiment and efficacy estimands (Section 3), similar to the primary objective.

Analysis of change from baseline in body weight and FSG at Week 40 will be conducted in a manner similar to the primary efficacy analyses (Section 9.3.1). Baseline HbA1c category [$\leq 8.5\%$ (≤ 69 mmol/mol) or $> 8.5\%$ (> 69 mmol/mol)] and baseline of the corresponding variable will be added in the model for body weight and FSG.

Comparisons among treatments relative to the proportion of participants achieving the HbA1c target value of $< 7.0\%$ (< 53 mmol/mol), $\leq 6.5\%$ (≤ 48 mmol/mol), and $< 5.7\%$ (< 39 mmol/mol) at Week 40 will be conducted using a logistic regression analysis with terms: treatment, any past prior use (yes or no) of any antihyperglycemic medication and baseline HbA1c as a covariate.

9.3.6. Safety Analyses

Safety assessments will be done using SS dataset (See section 9.2) irrespective of adherence to study intervention or initiation of rescue therapy. Selected safety analyses may be conducted after excluding data after the introduction of another antihyperglycemic therapy.

Adverse events will be coded from the actual term using the Medical Dictionary for Regulatory Activities (MedDRA) and reported with preferred terms and system organ class. Selected notable AEs of interest may be reported using high-level terms or Standardized MedDRA Queries.

Summary statistics will be provided for incidence of TEAEs, SAEs, study discontinuation due to AEs, study intervention discontinuation due to AEs, deaths, and other cardiovascular endpoints. Counts and proportions of participants experiencing AEs will be reported for each treatment group, and Fisher's exact test will be used to compare the treatment groups.

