- have been treated with insulin 1 year preceding Visit 1 and between Visit 1 and Visit 3; or have been treated with any antihyperglycemic medication 90 days preceding Visit 1 and between Visit 1 and Visit 3

Note: An exception is for the use of insulin for gestational diabetes or short-term use (≤ 14 days) for certain clinical situations such as acute illness, hospitalization, or elective surgery

- have history of chronic or acute pancreatitis prior to Visit 1
- be currently requiring or receiving treatment for diabetic retinopathy and/or macular edema
- have been treated with prescription drugs or similar other body weight loss medications including over-the-counter (OTC) medications that promote weight loss within 90 days prior to Visit 1 and/or between Visit 1 and Visit 3
- have been receiving chronic (>2 weeks or 14 days) systemic glucocorticoid therapy (excluding topical, intraocular, intranasal, or inhaled preparations) or had received such therapy within 30 days of Visit 1 or between Visits 1 and 3.

Number of Participants:

[figure not shown]
Approximately 200 participants (50 participants per arm) will be randomized in a **CCI** ratio (tirzepatide 5 mg once weekly [QW], tirzepatide 10 mg QW, tirzepatide 15 mg QW, and placebo QW).

Ethical Considerations of Benefit/Risk:

Considering the data that are available to date from previous clinical studies, and the measures taken to ensure the safety of the participants in this study, the potential risks related with tirzepatide are justified by the anticipated benefits a participant with T2DM may experience in the study.

Data Monitoring Committee: No

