2.3.1. Risk Assessment

Study Intervention

The most commonly reported treatment-emergent adverse events (TEAEs) observed in the tirzepatide clinical studies, in healthy participants and participants with T2DM, are gastrointestinal effects, including nausea, diarrhea, and vomiting.

Most were mild to moderate in severity and tended to occur during the dose escalation period.

Potential risks associated with tirzepatide include:

- acute pancreatitis
- increases in pulse rate
- hypoglycemia
- hypersensitivity reactions
- thyroid C-cell effects (only observed in rodents), and
- developmental (pregnancy) safety.

More detailed information about the adverse events of special interest may be found in Section 8.3.4 or in the IB.

Study Procedures

For the safety consideration of the participants in the placebo group, the following procedures and measures are planned.

- Participants must have HbA1c of $\geq 7.0\%$ (≥ 53 mmol/mol) to $\leq 9.5\%$ (≤ 80 mmol/mol) and have not used any antihyperglycemic medication during the 90 days preceding Visit 1.
- Participants will be provided with diet and exercise guidance during the whole study.
- Participants will receive a glucometer and training on how to perform self-monitoring of blood glucose (SMBG). Also they will be provided diaries and trained as appropriate to record BG values and hypoglycemic events. Participants will also be trained on disease management (symptoms of hypoglycemia and hyperglycemia) and study procedures.
- If participants fulfill the criteria for severe persistent hyperglycemia (See Section 6.9.1.1), rescue therapy will be started.

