6.1.1. Study intervention

This table lists the interventions used in this clinical study.

| Intervention Name | Tirzepatide 5 mg | Tirzepatide 10 mg | Tirzepatide 15 mg | Placebo |
|--------------------------------|--------------------------|--|--|---------|
| Dosage Level(s) | 2.5 mg QW 5 mg QW | 2.5 mg QW 5 mg QW 7.5 mg 10 mg QW | 2.5 mg QW 5 mg QW 7.5 mg 10 mg QW 12.5 mg QW 15 mg QW | NA |
| Route of Administration | SC | | | |
| Use | Investigational compound | | | |
| Drug formulation | SDP | | | |

Abbreviations: NA=not applicable; QW=once weekly; SDP= single-dose pen; SC=subcutaneous.

Tirzepatide dosing

The starting dose of tirzepatide will be 2.5 mg QW for 4 weeks, followed by an increase to 5 mg QW, for the duration of the study for the 5-mg group.

For the 10-mg group, the starting dose of tirzepatide will be 2.5 mg QW for 4 weeks, then the dose will be increased by 2.5 mg every 4 weeks (2.5 mg to 5 mg to 7.5 mg to 10 mg) until the 10-mg dose is reached and maintained for the duration of the study.

For the 15-mg group, the starting dose of tirzepatide will be 2.5 mg QW for 4 weeks, then the dose will be increased by 2.5 mg every 4 weeks (2.5 mg to 5 mg to 7.5 mg to 10 mg to 12.5 mg to 15 mg) until the 15-mg dose is reached and maintained for the duration of the study.

Placebo dosing

Participants randomized to the placebo group will inject matched placebo QW for the entire treatment period.

Timing of doses of study intervention

There are no restrictions on the time of day each weekly dose of study intervention is given, but it is advisable to administer the subcutaneous injections on the same day and same time each week, with or without meals. The actual date and time of all dose administrations will be recorded by the participant. If a dose of study intervention is missed, the participant should take it as soon as possible unless it is within 72 hours of the next dose, in which case, that dose should be skipped and the next dose should be taken at the appropriate time. The day of weekly administration can be changed if necessary, as long as the last dose was administered 72 or more hours before.

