There will be 2 estimands of interest in evaluating primary and secondary efficacy objectives. First estimand, the “treatment regimen” estimand, represents the efficacy irrespective of adherence to investigational product or introduction of rescue therapy for persistent severe hyperglycemia. Analysis relative to “treatment-regimen” estimand will be conducted using full analysis set. Second estimand, the “efficacy” estimand, represents efficacy prior to discontinuation of study drug or initiating rescue therapy for persistent severe hyperglycemia. Analysis relative to “efficacy” estimand will be conducted using efficacy analysis set. Safety will be assessed using safety analysis set. Selected safety analyses may be conducted after excluding data on rescue therapy or data after starting another antihyperglycemic medication.

End of study participation for a patient will be the earliest of date of death, date of withdrawal from further participation in the study, or date of safety follow-up visit (visit 801). For patients considered to be lost to follow-up, end of study participation will be the date of lost to follow-up reported by the investigator. Patient data included in database after the last date of study participation (date of death, date of early termination, or date of safety follow-up) will be excluded from statistical analysis. Listing of such data may be provided.

Summary statistics for continuous measures will include sample size, mean, standard deviation (SD), median, minimum, and maximum. Summary statistics for categorical measures (including categorized continuous measures) will include sample size, frequency, and percentages. Fisher’s exact test will be used to examine the treatment difference in categorical outcomes. Logistic

regression may be used to examine the treatment difference in binary efficacy outcomes. The negative binomial regression model will be used for the treatment comparison of discrete count measures if deemed appropriate.

The Kaplan-Meier method will be used for estimation of cumulative event-free rates over time, and cox proportional hazards regression analysis will be used to compare hazard rates among treatments.

Statistical treatment comparisons will only be performed between tirzepatide doses and placebo. Since the trials are not adequately powered to detect differences among tirzepatide doses, comparison among tirzepatide arms will not be performed unless otherwise specified.

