4.11. Safety Analyses

Unless specified otherwise, safety assessments will be based on the SS (see Section 3). All events that occur between the date of first dose of study drug to the date of patient's safety follow-up visit or patient's end of study participation will be included. Selected safety analyses may be conducted after excluding data after the introduction of another antihyperglycemic therapy. For rare events (<10 patients have the events), summary tables may not be generated, and individual patient level data will be listed.

Unless specified otherwise, comparisons of tirzepatide doses to placebo will be performed. For selected continuous safety parameters, difference among treatment mean change from baseline at scheduled visits will be assessed via a MMRM using REML. The model will include baseline HbA1c ($\leq 8.5\%$, $> 8.5\%$ [≤ 69 , > 69 mmol/mol]), any past prior use (yes or no) of any antihyperglycemic medication, treatment group, visit, treatment-by-visit interaction, baseline

value of the safety parameter and baseline of the safety parameter-by-visit interaction. To model the covariance structure within patients, the unstructured covariance matrix will be used. If this model fails to converge, the covariance structures specified in Section 4.8.3 will be tested in order.

For selected safety parameters, time-to-first-event analysis via cox-proportional hazards model may be conducted. For patients experiencing an event, “time-to-first-event” will be the time to the first occurrence of the event. For patients without the event, “time-to-event” will be censored at end of study participation (study discontinuation, safety follow-up visit, or date of death).

Where specified, rate of events will be analyzed using a generalized linear mixed-effects model assuming the number of events follow a negative binomial distribution, and with treatment as a fixed effect. The logarithm of years in specified time interval will be adjusted as an offset to account for possible unequal treatment duration in specified time interval between patients.

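### Safety incidence is compared only dose by dose (50 v 50); a supplementary pooled tirzepatide estimate (150 v 50) would cheaply sharpen the estimate of any harm common to all doses

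*Protocol*

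**What the plan says.** **Sample size.** Protocol 1.1: "Approximately 200 participants (50 participants per arm) will be randomized in a" ratio that is redacted. The arms are tirzepatide 5, 10 and 15 mg and placebo.

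**Comparisons.** Protocol 9.3.6 on reporting: "Counts and proportions of participants experiencing AEs will be reported for each treatment group". On testing, it adds that "Fisher's exact test will be used to compare the treatment groups". That section does not say whether the tests are pairwise. The SAP settles it. Section 4.1: "Statistical treatment comparisons will only be performed between tirzepatide doses and placebo". Section 4.11, for safety: "Unless specified otherwise, comparisons of tirzepatide doses to placebo will be performed". No pooled tirzepatide group is named in either document. Several tables in SAP 4.11.2 order events by a total column, whose content is not defined and to which no test or interval is attached.

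**Dosing.** Protocol 6.1.1, for the 5 mg arm: "The starting dose of tirzepatide will be 2.5 mg QW for 4 weeks, followed by an increase to 5 mg QW". The 10 and 15 mg arms also start at 2.5 mg and rise by 2.5 mg every 4 weeks.

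**Timing of events.** Protocol 2.3.1 says of the most commonly reported, gastrointestinal, events that most "tended to occur during the dose escalation period".

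**Role of inference.** The general rule in Protocol 9.3.1 is that "all tests of treatment effects will be conducted at a 2-sided alpha level of 0.05". SAP 4.11 then says that safety p-values and confidence intervals are not used for hypothesis testing, but to convey strength of evidence and uncertainty.

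**The concern.** For the first 8 weeks the plan takes 150 participants on one scheduled regimen, divides them by a label that has not yet changed what they receive, and compares each third with placebo. Differences among the active arms in that period should reflect chance and adherence, not dose. The reader gets three imprecise estimates of the same quantity and no summary of them.

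After Week 8 the doses diverge, but a harm that does not depend on dose, such as a hypersensitivity reaction to the molecule, is still one quantity estimated three times. The prespecified output gives no single estimate with its interval, and for an event not seen on tirzepatide it gives no bound based on all 150 exposed participants.

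**Working it through.** The documents state no power, event rate or detectable difference for any safety comparison, so there is no figure of the plan's own to reproduce beyond 4 × 50 = 200. All event rates below are assumptions.

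**1. Shared dosing (Protocol 4.1 and 6.1.1)**

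| Weeks | 5 mg arm | 10 mg arm | 15 mg arm |
|---|---|---|---|
| 0-4 | 2.5 | 2.5 | 2.5 |
| 4-8 | 5 | 5 | 5 |
| 8-12 | 5 | 7.5 | 7.5 |
| 12-16 | 5 | 10 | 10 |
| 16-20 | 5 | 10 | 12.5 |
| from 20 | 5 | 10 | 15 |

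All three arms match for 8 of 40 treatment weeks, or 8 of about 44 with the 4-week follow-up. The 10 and 15 mg arms match to Week 16.

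**2. Precision of the risk difference.** SE = √[p₁(1−p₁)/n₁ + p₀(1−p₀)/50]. With p₁ = p₀ the ratio of pooled to single-dose SE is √[(1/150 + 1/50)/(1/50 + 1/50)] = √(0.02667/0.04) = 0.816, an interval about 18% narrower. Where the tirzepatide rate exceeds placebo the gain can be larger. At 12% v 2%:
- single dose: √(0.1056/50 + 0.0196/50) = 5.0 percentage points
- pooled: √(0.1056/150 + 0.0196/50) = 3.3 percentage points

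**3. Bound after zero events.** The Clopper-Pearson two-sided 95% upper limit is 1 − 0.025^(1/n). For n = 50 it is 7.1%; for n = 150 it is 2.4%.

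**4. Chance that a contrast reaches p ≤ 0.05 in the direction of harm.** Fisher's exact test, two-sided 0.05, by full enumeration, allowing for the shared placebo arm.

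| Placebo | Tirzepatide 5/10/15 mg | One dose arm | At least one of three | Pooled |
|---|---|---|---|---|
| 2% | 10/10/10% | 19% | 41% | 43% |
| 2% | 12/12/12% | 31% | 59% | 62% |
| 2% | 15/15/15% | 51% | 79% | 82% |
| 5% | 15/15/15% | 24% | 47% | 46% |
| 5% | 20/20/20% | 51% | 78% | 76% |
| 2% | 4/8/12% | 1%, 9%, 31% by dose | 36% | 23% |
| 2% | 2/2/14% | <1%, <1%, 44% by dose | 44% | 7% |

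**5. Agreement among the three contrasts.** With the same true rate in every dose, all three reach p ≤ 0.05 in 7% of trials (2% v 12%), 22% (2% v 15%) and 24% (5% v 20%). At 2% v 12%, 59% − 7% = 52% of trials would flag a common harm in only one or two doses.

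**6. Rare events.** SAP 4.11 allows events in fewer than 10 patients to be listed instead of tabulated. The most extreme split below that threshold, 9/150 v 0/50, gives a pooled Fisher p of 0.116.

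**The case against.** **Does the plan miss harms because it does not pool?** A reader might infer this by setting one 50 v 50 contrast beside the pool: 31% against 62% at 2% v 12% looks like half the power. The documents do not support that reading. Three contrasts are read side by side, and no multiplicity adjustment is described for safety. Against at least one of three, the pool gains 2 to 3 points at a placebo rate of 2% and loses 1 to 2 points at 5%. The 50-person placebo arm is the main limit, and pooling does not enlarge it. To speak of a harm being missed also presumes a significance rule, which SAP 4.11 disclaims for safety.

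**Pooling can hide a dose-related harm.** This stands, and the last two rows of the table show how badly. It rules out replacing the dose columns, which match the stated safety objective in SAP 1.1. It does not rule out a column beside them.

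**Much is already covered.** SAP 4.11.2 plans risk differences with 95% CIs for events at or above 5%. SAP 4.11.4.13 plots the time course of nausea, vomiting and diarrhea by treatment. SAP 4.1 permits further analyses. This stands in part: none of it prespecifies a pooled estimate, and one chosen after unblinding is open to selective use.

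**The reach is limited.** This also stands. Identical dosing covers 8 of about 44 weeks, and the clustering statement concerns gastrointestinal events only. Hypoglycemia is analysed in SAP 4.11.4.1 by logistic regression, with a possible negative binomial model for rates, so the Fisher figures do not describe it. Pancreatic and other rare events may only be listed.

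**Conclusion.** The point holds as a cheap improvement, not as an error or contradiction in the plan. The SAP restricts comparisons to each dose against placebo and prespecifies no pooled estimate. A harm common to all doses is therefore estimated less precisely than the data allow: the pooled standard error is 0.816 times the single-dose one at equal rates, and the zero-event bound is 2.4% instead of 7.1%. A pooled estimate would also give one answer where the three contrasts would often disagree by chance.

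The case is strongest for Weeks 0-8 and for gastrointestinal events. It does not extend to a claim that the plan would fail to flag real harms that pooling would catch.

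These results assume 50 treated participants per arm, adherence to the scheduled doses in Weeks 0-8 and, for the power and agreement figures, the assumed event rates. The 0.816 ratio needs only equal rates, and the zero-event bounds need only the group sizes.

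**What to change.** In SAP 4.11, with a matching sentence in Protocol 9.3.6 and an exception in SAP 4.1:

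- Keep the three dose columns and their comparisons with placebo as the main display.
- Prespecify a supplementary pooled tirzepatide column, with a risk difference against placebo and a 95% CI, for the main incidence endpoints that are tabulated: TEAEs, SAEs, discontinuation due to adverse events, gastrointestinal TEAEs and hypersensitivity.
- Show it for the whole safety period and separately for events starting in Weeks 0-8.
- State that it is supplementary and is read beside the dose-specific results.
- Define the total column in the SAP 4.11.2 tables: whether it holds all participants or only those on tirzepatide.

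The cost is SAP wording, one extra column and one extra time window; no change to data collection, visits, dosing or sample size is needed. The downside is that after Week 8 the pooled figure averages over different doses and can mask a dose-related effect, so it should never be shown alone.
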